# **Clinical Study Protocol**

## **Johnson & Johnson Vision Care, Inc.**

### **5.2. Masking**

Phase 1: Not Applicable. Subjects are wearing their habitual contact lenses.

Phase 2: This is a double-masked trial. Masking will be used to reduce potential bias. Subjects will be unaware of the identity of the investigational product. Investigators involved in the data collection of the endpoints will be masked as to the identity of the investigational product.

### **5.3. Procedures for Maintaining and Breaking the Masking**

Every attempt will be made to keep the clinical trial personnel involved in the study (e.g. data management, biostatistician and clinical operations) unaware of the identity of the assigned study lenses. The identity of the study lenses will be masked by having the blister packs labeled with the study number, lot number, sphere power, expiration date and the randomization codes. Only the unmasked biostatistician generating the lens fitting schedule will have access to the decode information that allows matching of the randomization codes to the test articles. The medical monitor will also have access to the decode information in case breaking the mask is necessary for the urgent medical treatment of a subject.

Under normal circumstances, the mask should not be broken until all subjects have completed the study and the database is finalized. Otherwise, the mask should be broken only if specific emergency treatment/course of action would be dictated by knowing the treatment status of the subject. In such cases, the investigator may, in an emergency, contact the medical monitor. In the event the mask is broken, the sponsor must be informed as soon as possible. The date, time, and reason for the unmasking must be documented in the subject record. The investigator is also advised not to reveal the study treatment assignment to the clinical site or sponsor personnel.

Subjects who are discontinued will be replaced.

## **6. STUDY INTERVENTION**

The following contact lenses will be used in Phase 2 of this study:

Table 2: Test Articles for Phase 2

	Test	Control
Name	TRP-200	AV OASYS 1-Day
Manufacturer	JJVC	JJVC
Lens Material	senofilcon A (C3)	senofilcon A (C3)
Nominal Base Curve @ 22°C	8.5	8.5
Nominal Diameter @ 22°C	14.3	14.3
Nominal Distance Powers (D)	-1.00 through -6.00	-1.00 through -6.00
Water Content (Optional)	38	38
Center Thickness	0.085	0.085

# Clinical Study Protocol

## Johnson & Johnson Vision Care, Inc.

	Test	Control
Oxygen Permeability (Dk)	103	103
Wear Schedule in Current Study	Daily	Daily
Replacement Frequency	Daily	Daily
Packaging Form (vial, blister, etc.)	Blister	Blister
New UV/HEV-blocker	Yes	No

Approximately 40 lenses per stock keeping unit (SKU) will be provided based on 66 subjects, 1-period, contralateral, non-dispensing design, US population normalized for peak SKUs.

### 6.1. Ancillary Supplies/Products

The following solutions will be used in this study. RevitaLens may be used to temporarily store contact lenses prior to biomicroscopy or to return any lenses that are found or thought to have a defect.

Table 3: Ancillary Supplies for Phase 2

Solutions				
Solution Name/Description	Acuvue™ RevitaLens Multipurpose Solution	Single use Eye-Cept® Rewetting Drops	LaciPure Saline Solution	ScleralFil Preservative Free Saline Solution
Manufacturer	Johnson & Johnson Vision	Optics Laboratory	Menicon	Bausch & Lomb
Preservative	alexidine dihydrochloride 0.00016% and polyquaternium-1 0.0003%	None	None	None

Lens cases and fluorescein strips (either 0.6 mg or 1.0 mg) will be supplied for use as needed.

### 6.2. Administration of Test Articles

Phase 2: Test articles will be dispensed to subjects meeting all eligibility requirements, including any dispensing requirements set forth in this clinical protocol. Subjects will be dispensed an adequate supply of test articles to complete the study. Lost or damaged test articles may be replaced at the discretion of the investigator and/or the sponsor.

[figure not shown]
### 6.3. Packaging and Labeling

Phase 2: The study articles will be packaged in blisters as the primary packaging. The study article will be over-labeled to mask the subject and investigators to the identity of the lens. The study articles will be in plastic bags as the secondary packaging form. The sample study label is shown below (Figure 11).

# Clinical Study Protocol

## Johnson & Johnson Vision Care, Inc.

Figure 11: Representative image of the primary and secondary packaging for Phase 2.

### 6.4. Storage Conditions

Phase 2: Test articles will be maintained at ambient temperatures at the clinical site. Test articles must be kept under secure conditions.

### 6.5. Collection and Storage of Samples

No samples will be collected as part of the study procedures.

When possible for Phase 2, any lens or test article associated with an Adverse Event and/or a Product Quality Complaint must be retained and stored in a glass vial with moderate solution pending directions from the sponsor for potential return to JJVC.

### 6.6. Accountability of Test Articles

Phase 2: JJVC will provide the Investigator with sufficient quantities of study articles and supplies to complete the investigation. The Investigator is asked to retain all lens shipment documentation for the test article accountability records.

Test articles must be kept in a locked storage cabinet, accessible only to those assigned by the Investigator for dispensing. The Investigator may delegate this activity to authorized study site personnel listed on the Site Delegation Log. All test articles must be accounted. This includes:

1. What was dispensed for the subject for trial fitting, to wear out of the office, or issued for the subject to replace appropriately between visits.
2. What was returned to the Investigator unused, including expired or malfunctioning product.
3. The number and reason for unplanned replacements.

# **Clinical Study Protocol**

## **Johnson & Johnson Vision Care, Inc.**

The Investigator will collect all unused test articles from the subjects at the end of the subject's participation. Subject returned unused test articles must be separated from the clinical study inventory of un-dispensed test articles and must be labeled with the subject number and date of return. Following final reconciliation of test articles by the monitor, the Investigator or monitor will return all unused test articles to JJVC.

If there is a discrepancy between the shipment documents and the contents, contact the study monitor immediately.

## **7. STUDY EVALUATIONS**

### **7.1. Time and Event Schedule**

Table 4: Time and Events

Visit Information	PHASE 1 Visit 1 Screening, Baseline, Assessment Final Evaluation	PHASE 2 Visit 1 Screening, Baseline, Fitting / Assessment Final Evaluation
Time Point	Day 0	Day 0
Estimated Visit Duration	1.0 hours	3.0 hours
Statement of Informed Consent	X	X
Demographics	X	X
Medical History/Concomitant Medications	X	X
Habitual Contact Lens Information	X	X
Eligibility Following Screening	X	X
Entrance Visual Acuity	X	X
Subjective Sphero-Cylindrical Refraction and best-corrected VA		X
Eye Dominancy		X
Slit Lamp Biomicroscopy	X	X
Eligibility Following Baseline Evaluation	X	X
Lens Selection		X
Lens Insertion & Settling		X
Visual Acuity and Over Refraction		X
Lens Power Modification (if applicable)		X
Subject Reported Ocular Symptoms		X
Visual Acuity		X
General Fit Assessment		X

**Clinical Study Protocol**  
**Johnson & Johnson Vision Care, Inc.**

Visit Information	PHASE 1 Visit 1 Screening, Baseline, Assessment Final Evaluation	PHASE 2 Visit 1 Screening, Baseline, Fitting / Assessment Final Evaluation
Time Point	Day 0	Day 0
Estimated Visit Duration	1.0 hours	3.0 hours
Vision Assessments: photopic and mesopic contrast sensitivity	X	
Vision Assessments: photopic and mesopic contrast sensitivity, photopic resolution acuity		X
Exit Snellen Distance Visual Acuity	X	X
Study Completion	X	X

## 7.2. Detailed Study Procedures

### PHASE 1: VISIT 1

Subjects must enter the study wearing their habitual contact lenses.

Phase 1: Visit 1: Screening			
Step	Procedure	Details	
1.1	Statement of Informed Consent	Each subject must read, understand, and sign the Statement of Informed Consent before being enrolled into the study. The Principal Investigator or his/her designee conducting the informed consent discussion must also sign the consent form.  Note: The subject must be provided a signed copy of this document.	
1.2	Demographics	Record the subject's year of birth, age, gender, race and ethnicity.	
1.3	Medical History and Concomitant Medications	Record the subject's medical history and concomitant medications.	
1.4	Habitual Lenses	Record the subject's habitual lens type, parameters, lens care solution, wear modality, duration of lens wear, and approximate prescription date. The subject's spherical contact lens powers must be between -1.00 D and -6.00 D inclusive.	

**Clinical Study Protocol**  
**Johnson & Johnson Vision Care, Inc.**

Phase 1: Visit 1: Screening		
Step	Procedure	Details
1.5	Eligibility after Screening	
All responses to Screening Inclusion Criteria questions must be answered “yes” and all responses to Exclusion Criteria must be answered “no” for the subject to be considered eligible.
 
If subject is deemed to be ineligible after screening, proceed to Final Evaluation and complete Subject Disposition. Refraction and Biomicroscopy forms do not need to be completed as part of Final Evaluation.

Phase 1: Visit 1: Baseline		
Step	Procedure	Details
1.6	Entrance Visual Acuity	Record the distance Snellen visual acuity (OD, OS, and OU) to the nearest letter with their habitual contact lenses. Subjects must read the smallest line until at least 50% of the letters are read incorrectly. Subjects must demonstrate a minimum of 20/20 visual acuity OD and OS to continue.
1.7	Temporary Lens Removal	The subjects habitual contact lenses will be removed and temporarily stored in a contact lens case with RevitaLens or saline.
1.8	Slit Lamp Biomicroscopy	
FDA Slit Lamp Classification Scale will be used to grade the findings.
 
If any of these slit lamp findings are grade 3 or higher, the subject may not continue at this time, but may return up to one additional time to determine eligibility. If discontinued a final examination must be completed.
 
If the clearance of the fluorescein needs to be expedited, preservative-free rewetting drops or saline may be instilled.

1.9	Lens Reinsertion	The subject’s habitual contact lenses removed in step 1.7 will be reinserted.

**Clinical Study Protocol**  
**Johnson & Johnson Vision Care, Inc.**

Phase 1: Visit 1: Baseline		
Step	Procedure	Details
1.10	Eligibility after Baseline	
All responses to Inclusion Criteria questions must be answered “yes” and all responses to Exclusion Criteria questions must be answered “no” for the subject to be considered eligible.
 
If subject is deemed to be ineligible after baseline, proceed to Final Evaluation and complete Subject Disposition. Refraction and Biomicroscopy forms do not need to be completed as part of Final Evaluation.

**Clinical Study Protocol**  
**Johnson & Johnson Vision Care, Inc.**

Phase 1: Visit 1: Assessments		
Step	Procedure	Details
1.11	Visual Performance Testing Without Glare	
Visual performance testing will be performed using the Metropsis system OD in the following order. The left eye will be patched.
 
Without glare OD:
 
 
1. Photopic contrast sensitivity           
 
A. Test distance: 1.5 m
 
B. Screen luminance approximately 120 cd/m^2
 
C. Ambient luminance must be dark with no lights or reflective surfaces within the general field of view of the target
 
D. Spatial frequency: 6 cpd using a 2 degree Gabor stimulus. EDC to record: contrast threshold mean +/- SD for each spatial frequency. Range 0.0000 – 100.0000.
 
E. Rest a minimum of 5 minutes before next test
 
 
 
2. Mesopic contrast sensitivity           
 
A. Test distance: 1.5 m
 
B. Screen luminance approximately 3 cd/m^2. This will be achieved by placing neutral density films over the Metropsis monitor.
 
C. Ambient luminance must be dark with no lights or reflective surfaces within the general field of view of the target
 
D. Spatial frequency: 6 cpd using a 2 degree Gabor stimulus. EDC to record: contrast threshold mean +/- SD for each spatial frequency. Range 0.0000 – 100.0000.
 
E. Rest a minimum of 2 minutes before next test
 
 
 

**Clinical Study Protocol**  
**Johnson & Johnson Vision Care, Inc.**

Phase 1: Visit 1: Assessments		
Step	Procedure	Details
1.12	Visual Performance Testing With Glare	
Visual performance testing will be performed using the Metropsis system OD in the following order. The left eye will be patched. The spectral output and intensity of the broadband light source will be verified before each test. Subjects recording an increase in contrast sensitivity with the glare source will be discontinued per ANSI Z80.12-2007.
 
With glare OD:
 
 
1. Photopic contrast sensitivity             
 
A. Test distance: 1.5 m
 
B. Screen luminance approximately 120 cd/m^2
 
C. Ambient luminance must be dark with no lights or reflective surfaces within the general field of view of the target.
 
D. Spatial frequency: 6 cpd using a 2 degree Gabor stimulus. EDC to record: contrast threshold mean +/- SD for each spatial frequency. Range 0.0000 – 100.0000.
 
E. Rest a minimum of 5 minutes before next test
 
 
 
2. Mesopic contrast sensitivity             
 
A. Test distance: 1.5 m
 
B. Screen luminance approximately 3 cd/m^2
 
C. Add a 0.52 log unit ND filter to glare source
 
D. Ambient luminance must be dark with no lights or reflective surfaces within the general field of view of the target
 
E. Spatial frequency: 6 cpd using a 2 degree Gabor stimulus. EDC to record: contrast threshold mean +/- SD for each spatial frequency. Range 0.0000 – 100.0000.
 
 
 

# Clinical Study Protocol

## Johnson & Johnson Vision Care, Inc.

### **PHASE 1: VISIT 1: Final Evaluation**

The subject will complete the same Final Evaluation form as those subjects completing phase 2 of the study. Phase 1 subjects will need to temporarily remove their habitual contact lenses during the Final Evaluation slit lamp exam.

### **PHASE 2: VISIT 1**

The subjects must present to Phase 2: Visit 1 wearing spectacles, not having worn contact lenses on the day of the visit.

Phase 2: Visit 1: Screening			
Step	Procedure	Details	
1.13	Statement of Informed Consent	
Each subject must read, understand, and sign the Statement of Informed Consent before being enrolled into the study. The Principal Investigator or his/her designee conducting the informed consent discussion must also sign the consent form.
 
Note: The subject must be provided a signed copy of this document.
	
1.14	Demographics	Record the subject's year of birth, age, gender, race and ethnicity.	
1.15	Medical History and Concomitant Medications	Record the subject's medical history and concomitant medications.	
1.16	Habitual Lenses	Record the subject's habitual lens type, parameters, lens care solution, wear modality, duration of lens wear, and approximate prescription date.	
1.17	Eligibility after Screening	
All responses to Screening Inclusion Criteria questions must be answered "yes" and all responses to Exclusion Criteria must be answered "no" for the subject to be considered eligible.
 
If subject is deemed to be ineligible after screening, proceed to Final Evaluation and complete Subject Disposition. Refraction and Biomicroscopy forms do not need to be completed as part of Final Evaluation.
	

**Clinical Study Protocol**  
**Johnson & Johnson Vision Care, Inc.**

Phase 2: Visit 1: Baseline		
Step	Procedure	Details
1.18	Entrance Visual Acuity	Record the distance Snellen visual acuity (OD, OS, and OU) to the nearest letter with their habitual spectacle. Subjects must read the smallest line until at least 50% of the letters are read incorrectly.
1.19	Subjective Sphero-cylindrical Refraction	Complete subjective sphero-cylindrical refraction and record the resultant distance visual acuity (OD, OS, and OU) to the nearest letter.
1.20	Eye Dominancy	The investigator will determine eye dominancy of the subject by first using the +1.00 blur test. If this fails to determine dominancy, then the sighting test will be used.
1.21	Slit Lamp Biomicroscopy	
FDA Slit Lamp Classification Scale will be used to grade the findings.
 
If any of these slit lamp findings are grade 3 or higher, the subject may not continue at this time, but may return up to one additional time to determine eligibility. If discontinued a final examination must be completed.
 
If the clearance of the fluorescein needs to be expedited, preservative-free rewetting drops or saline may be instilled.

1.22	Eligibility after Baseline	
All responses to Inclusion Criteria questions must be answered “yes” and all responses to Exclusion Criteria questions must be answered “no” for the subject to be considered eligible.
 
If subject is deemed to be ineligible after baseline, proceed to Final Evaluation and complete Subject Disposition. Refraction and Biomicroscopy forms do not need to be completed as part of Final Evaluation.

**Clinical Study Protocol**  
**Johnson & Johnson Vision Care, Inc.**

Phase 2: Visit 1: Treatment 1 Lens Fitting		
Step	Procedure	Details
1.23	Lens Selection	
Assign the study lens based on the randomization scheme provided by the biostatistician.
 
Select the contact lens power [REDACTED] based on vertexed spherical equivalent from the refraction.

1.24	Lens Insertion	
The Investigator or the subject inserts the study lenses. Record the time of lens insertion.
 
Check for lens damage under the slit lamp before proceeding with lens settling.
 
Replace damaged lenses if applicable.
 
Ensure the subject is given a Patient Instruction Guide.

1.25	Lens Settling	Allow the study lenses to settle for a minimum of 5 minutes.
1.26	Subjective Best Sphere Over Refraction	Perform subjective best sphere refraction over the study lenses (adopt the maximum plus to maximum visual acuity (MPMVA) approach).
1.27	Lens Power Modification (if applicable)	
Adjust the lens power if the subject's best sphere over-refraction is not plano.
 
For each power modification, select the adjusted fitting lens power as appropriate and repeat steps 1.12 through 1.14.
 
Up to two power modifications are allowed per eye.

1.28	Subject Reported Ocular Symptoms	Subjects will respond to a verbal open-ended symptoms questionnaire.
1.29	Visual Acuity	Record the best corrected Snellen distance visual acuity to the nearest letter (OD and OS). Subjects must read the smallest line until at least 50% of the letters are read incorrectly. Visual acuity with the study contact lenses must be 20/30 or better OD and OS.

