## **Clinical Study Protocol**

### **Johnson & Johnson Vision Care, Inc.**

observed that there is a ubiquity of HEV filters throughout nature and they appear to serve several major functions that manifest throughout life: they improve image quality (e.g., reducing chromatic aberration); reduce glare disability and discomfort (“dazzle” often referred to as positive dysphotopsia); increase visual range (reduction of blue haze); and chromatic contrast. Hundreds of studies have now confirmed (using a variety of experimental designs) that ocular filters (ranging from natural macular pigments to tinted contact lenses and cataract implants) serve these functions in human vision.

Although there is wide agreement that strategic filtering improves visual performance under a wide variety of circumstances, why do some studies produce null results?

The key is that human biology evolved over millennia under real world (not artificial) conditions. In a field with few agreements, nutritional scientists widely agree that processed food is unhealthy and that eating a largely whole food plant-based diet is essential (i.e., the dietary conditions under which we evolved). Visual performance is often tested under largely contrived and artificial achromatic conditions. If, as the evidence overwhelmingly suggests, HEV filtering helps reduce glare issues or reduce the deleterious effects of blue haze, it certainly cannot do that if the stimulus (unlike the real world) contains very little short-wave light (Figure 4).

Note that most of the “artificial sources” shown have very little short-wave energy. Normal daylight (Figure 4, top left) has a correlated color temperature (CCT) of about 6000-6500K. The north sky, however, has a CCT of 10,000K (which means the HEV component dramatically increases). Often glare devices use fluorescents, halogens or tungsten light,

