# Clinical Study Protocol

## Johnson & Johnson Vision Care, Inc.

1. Within-subject evaluation of the impact of an HEV-absorbing contact lens compared to a standard transparent contact lens as assessed through CSF and acuity with and without a broadband glare source (n = 60).

Finally, the statement that “There is no accepted standardized method for glare testing” is largely true. There are several ISO standards that mention glare (e.g., 9358:1194, 14490-6:2014, 12646:2008), several CIE documents (e.g., 17-22-098, 17-22-103, 146:2002), several IES documents (<https://www.ies.org/?s=Glare>), and multiple ANSI standards that mention glare (<https://webstore.ansi.org/Search/Find?in=1&st=glare>) and none of them mention how a glare source should be consistently incorporated into visual performance testing. How close should the glare source be to the target? How close should the glare source be to the eye? How many glare sources should there be? How bright should the glare sources be? What should the spectral emission of the glare sources be? These uncertainties inevitably lead to inconsistencies from instruments to instruments, and subsequently, from studies to studies. ANSI Z80.12-2007 helps to clarify by stating that a small pilot investigation of young adult subjects with normal corneas and normal vision may be necessary to determine the appropriate glare level to reduce the mean contrast sensitivity by about 0.1 log units at 6 cpd.

The number of subjects that constitute “a small pilot” is debatable. The acceptable standard deviation that defines “about” 0.1 log units also unclear. Regardless, companies that manufacture glare testing instruments (e.g., M&S Technologies (Niles, IL, US), and Metropsis by Cambridge Research Systems (Rochester, UK)) have adopted this standard for all glare testing and this will be implemented in the study.

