### **4.2. Study Design Rationale**

Phase 1: This study phase is to help ensure that the intensity of the glare source is efficacious and satisfies ANSI Z80.12-2007. Subjects will wear their own contact lenses and be tested unilaterally.

Phase 2: This study phase will be executed using a contralateral design. There are several benefits to this choice of design. First, a contralateral design will allow us to compare performance within the same individual, ostensibly with the same baseline light sensitivity by eye. Second, other subject factors that can influence visual performance, such as iris color and absorption of test lights via macular pigment, are better controlled using this design. Third, in psychophysical testing, which is the gold standard for many of the visual functions being tested, participants make judgments about some event threshold, such as when an image disappears. Participants may have different criteria for threshold events that are internally consistent *within* subjects but can vary *between* subjects. A contralateral design allows the investigational lens to be compared within subjects, with consistent criteria for threshold events. Sufficient time will be taken between measures to reduce any potential bias, as follows:

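### Phase 2 masking covers the packaging and the codes but not the opened lenses, and step 1.24 lets the subject handle one Test and one Control lens side by side, which could unmask the between-eye comparison if the lenses look different

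*Combined protocol and SAP*

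**What the plan says.** Section 5.2 calls Phase 2 double-masked. It promises for subjects that "Subjects will be unaware of the identity of the investigational product", and makes a matching promise for investigators who collect endpoint data.

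Three measures are described:
- Section 5.3, on coded labels: "The identity of the study lenses will be masked by having the blister packs labeled with the study number, lot number, sphere power", followed by the expiration date and randomization codes.
- Section 6.3, on packaging: the article is "over-labeled to mask the subject and investigators to the identity of the lens".
- Section 5.3 also restricts the decode information to the unmasked biostatistician and the medical monitor.

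Once the blister is open, Section 7.2 step 1.24 applies: "The Investigator or the subject inserts the study lenses". The same step continues: "Check for lens damage under the slit lamp before proceeding with lens settling". Step 1.27 allows up to two power modifications per eye, step 1.30 assesses the fit of each lens, and step 1.32 replaces lost or damaged lenses at once. The endpoint tests follow in steps 1.33 and 1.34.

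On appearance, Section 1 describes the comparison as "an HEV-absorbing contact lens compared to a standard transparent contact lens". The Control package insert (Appendix C) says that lens is tinted blue for handling. The colour of the Test lens is not given in any readable text.

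**The concern.** The design is contralateral: each subject wears Test in one eye and Control in the other, both inserted at the same sitting. If the lenses differ in colour, a subject who inserts them sees the difference side by side and knows which eye received which. The measurements depend on the subject's own responses. Section 4.2 defends the design on the ground that "Participants may have different criteria for threshold events", which it takes to be consistent within a person. A belief that one eye has the better lens could disturb that consistency. Any resulting between-eye shift in effort or response enters the Test minus Control difference directly, and the Section 14.5 model (lens type, eye dominance, their interaction, age) has no term to separate it from a lens effect.

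At stake is the primary superiority claim, on which the secondary tests also depend through the gatekeeping in Section 14.4.

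**Working it through.** **1. Is a visible difference plausible?**
- HEV stands for High Energy Visible light. Section 1 places it in largely the same band as the blue-light hazard, about 400-500 nm, inside the 380-780 nm range to which the eye responds. It describes several natural HEV filters as yellow.
- Table 2 lists the two lenses as the same in material, base curve, diameter, powers, water content, thickness and Dk. Apart from the name, only the new blocker differs.
- The Control is not colourless, so only a difference in tint would tell the two apart.

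The text makes a difference plausible. It neither states nor excludes one.

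**2. Does any described measure act after the blister is opened?** Labels and over-labels are on the packaging. Decode restriction hides the code, not the lens. No readable text says that the lenses look alike, separates the person inserting them from the person testing, or keeps the subject from viewing them.

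**3. Reproducing the plan's power.** Inputs from Section 14.2 and Table 9: difference -0.05 logMAR, two-sided alpha 0.05, n = 60, paired t-test.

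SD of the difference = √(s₁² + s₂² − 2·r·s₁·s₂). For SDs 0.08/0.09 and r = 0.5: √(0.0064 + 0.0081 − 0.0072) = √0.0073 = 0.0854.

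| SD Test/Control | r | SD of difference | Power, Table 9 | Power, recomputed |
|---|---|---|---|---|
| 0.08/0.09 | 0.5 | 0.0854 | 99.4% | 99.4% |
| 0.08/0.09 | 0.3 | 0.1009 | 96.5% | 96.5% |
| 0.10/0.11 | 0.5 | 0.1054 | 95.1% | 95.1% |
| 0.10/0.11 | 0.3 | 0.1245 | 86.4% | 86.4% |

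The plan's power figures are correct, and the same SDs are used below.

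**4. Illustration: an assumed shift b favouring Test, with a true lens effect of zero.** The documents give no value for b, so 0.01, 0.02 and 0.03 logMAR are assumptions.

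Section 14.5 declares superiority if the upper 95% confidence limit is below 0. That probability is P(T > 2.001), where T is noncentral t with 59 df and noncentrality b / (SD/√60). For SD 0.0854 the standard error is 0.0854/√60 = 0.01103, so b = 0.02 gives noncentrality 1.813 and probability 43%. For SD 0.1245 the standard error is 0.01607, the noncentrality 1.244 and the probability 23%.

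| Assumed shift (logMAR) | Chance of meeting the superiority rule, SD 0.1245 to 0.0854 |
|---|---|
| 0 | 2.5% |
| 0.01 | 8.9% to 14.3% |
| 0.02 | 23% to 43% |
| 0.03 | 45% to 76% |

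**5. The clinical margin.** Sections 2.3 and 14.5 also compare the point estimate with -0.05 logMAR. The chance that the estimate reaches it is P(Z > (0.05 − b)/SE), normal approximation, and is largest at SD 0.1245:
- b = 0.01: 0.04/0.01607 = 2.489, about 0.6%
- b = 0.02: 0.03/0.01607 = 1.867, about 3.1%
- b = 0.03: 0.02/0.01607 = 1.244, about 10.7%

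**The case against.** A reader might infer that the Test lens is visibly tinted, so that step 1.24 breaks the mask. The documents do not support this. The phrase "ranging from natural macular pigments to tinted contact lenses and cataract implants" comes from a sentence about the general literature on ocular filters, not about the Test lens. The contrast with a transparent lens is loose, since the Control is itself tinted blue. The Investigator's Brochure, the label figure and several appendices cannot be read here and may describe appearance. Seeing a difference also does not by itself reveal which lens is Test.

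A reader might also infer that labels are the only protection. Decode access is restricted as well, and Section 5.1 lets a designee pull the lenses, so a separate handler is permitted, though not required.

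Nor is it shown that the Section 4.2 argument about personal criteria fits the primary endpoint. Its example is judging when an image disappears, whereas the primary task is Landolt C resolution, whose response rule is not in the readable text. How far expectation could move that result is unknown. An average shift over all 60 subjects would need widespread unmasking, correct guesses and a common direction of bias.

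These points stand, and they limit the conclusion to a conditional one. They do not answer the procedural gap: subjects are promised masking, the same subjects may handle both opened lenses, and nothing readable protects the mask at that moment.

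**Conclusion.** The concern holds in conditional form. The described masking does not conceal opened lenses, and step 1.24 allows the subject to handle one of each. If the lenses can be told apart by eye, this could unmask the between-eye comparison; whether they can is undocumented.

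The false-positive figures (9-14%, 23-43% and 45-76%) illustrate how sensitive the confidence-interval rule is to a small bias. They rest on assumed shifts, zero true effect, 60 completers and the Table 9 SDs, and they do not estimate the actual bias. A false result that also reached -0.05 logMAR would be much less likely: at most about 1%, 3% and 11%. A change is worth making because it costs little and protects the primary comparison if the lenses do differ.

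**What to change.** In step 1.24, remove the option for the subject to insert the lenses. Have the Investigator, or the designee who already pulls the lenses under Section 5.1, insert both and do the damage check, without the subject handling or viewing either lens off the eye. Apply the same rule to power-modified lenses (step 1.27) and replacements (step 1.32). Where the site already delegates lens handling, that person should not run the Metropsis tests for the same subject.

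The cost is a short text change and a few minutes of chair time; some habitual wearers may prefer to insert their own lenses. The step already permits insertion by the Investigator, so no new procedure is needed. Some cues remain: a subject may notice a tint during wear, and staff still see the lenses at the fit assessment in step 1.30.
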